## 8. Data Collection

- Demographics, medical history and physical examination will be performed at screening and baseline visit.
- Circulating measures: Subjects will report fasted for standard blood chemistry analysis at baseline, 1, 3, 6, 9 months and end of study. A venous blood gas (for pH and  $P_{CO_2}$ ) will be obtained at baseline and end of study to get a more complete description of the acid-base status of the participant. To assess participant's positive acid balance we will collect 24-hour urines at baseline, 6 months and end of study to measure net acid excretion and net endogenous acid production. A urine pregnancy test will be performed if clinically indicated at the screening visit.
- Outcome measures: FMDBA will be performed at baseline, 1 month (optional), 6 months and end of study. Aortic PWV will be performed at baseline, 6 months and end of study. LVMI will be performed at baseline and end of study. Plasma will be collected for measurement of AII, aldosterone and ET-1 and serum will be collected for measurement of  $T_{50}$ , at baseline, 1 month (if patient has in-person visit), 6 months and end of study.

- Other circulating markers of calcification: In addition, will measure serum fetuin-A (inhibitor of VC); serum calcium (promoter of VC); serum phosphate (promoter of VC); inflammatory markers (promoters of VC): serum C-reactive protein and cytokine 12 panel (IL-2, IL-4, IL-5, IL-6, IL-8, IL-10, IL-13, Interferon gamma, Interleukin 2 Receptor, Interleukin 1 beta, tumor necrosis factor); and markers of bone metabolism (serum parathyroid hormone, bone alkaline phosphatase, beta C-terminal telopeptide). These markers will be measured at baseline, 6 months and end of study.
- Resting BP: Arterial BP will be measured in triplicate while seated at rest using an automated oscillometric machine (Dinamap) at all in person study visits.
- Measures of adherence and safety:
  - Pill counts will be assessed at the quarterly visits and end of study to document subject adherence.
  - A GI symptoms questionnaire will be performed to assess tolerability of the intervention monthly (either via telephone or at an in person visit). Participants will be asked to rate symptoms of nausea, bloating, and diarrhea.
  - Adverse event assessment will be performed monthly either via telephone or at an in person visit. Additional telephone calls and PRN follow-up visits will occur at the discretion of the PI.

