## 7. Safety monitoring

**• Expected adverse events:** Sodium bicarbonate therapy may cause bloating, flatulence and abdominal discomfort. Although previous studies using similar doses of sodium bicarbonate have not reported significant changes in edema, body weight or BP, sodium bicarbonate may cause edema to develop or worsen thereby increasing BP. Previous studies suggest fluid retention is greater when sodium is accompanied by the chloride anion rather than the bicarbonate anion. As shown in our **preliminary data**, sodium bicarbonate did

not result in increased BP. Sodium bicarbonate also has the potential for causing metabolic alkalosis and hypokalemia if it is retained rather than excreted in the urine. These expected adverse events will be monitored during the course of the study and in general, can be medically managed by adjusting antihypertensive and/or diuretic agents, providing potassium replacement and by dietary changes. Of note, none of these adverse events were observed in our short-term pilot study.

- **Dose reduction and discontinuation:**

- Serum bicarbonate >28 mEq/L: The intervention dose (study drug) will be reduced by 50% by the PI and diuretics will be adjusted as appropriate by the primary nephrologist or PCP. The PI will contact the primary nephrologist or PCP by phone or email and discuss changes in diuretics. The participant will return for a visit one week later to have serum chemistries rechecked. If the bicarbonate remains >28 mEq/L the intervention will be stopped by the PI and the participant will have serum bicarbonate measured weekly until it is <28 mEq/L. Plasma ionized calcium will be checked if bicarbonate is >30 mEq/L at any visit since an increase in pH can decrease the ionized calcium concentration. Management of low ionized calcium will be at the discretion of the PI based on symptoms reported by the patient. The PI will contact the primary nephrologist or PCP if she believes calcium supplementation is necessary and the primary physician will order the medication.

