## 11. Statistical Analysis

- **General consideration:** The primary analysis will be conducted on ITT basis. Analysis of covariance (ANCOVA) with complete data will be the primary analysis for efficacy. Multiple imputation will apply because of missing data and sensitivity analysis will be conducted in various ways, including linear mixed effects model and pattern-mixture model approach. Compliance of intervention will be summarized using the number of pills taken as the proportion of planned number of pills. The association of compliance with each of the outcomes ( $FMD_{BA}$  aPWV and LVMI) will be explored using multiple linear regression. Participants who receive rescue therapy will be analyzed in the ITT analysis but excluded from the per-protocol analysis. We will also analyze the data with and without adjustment for change in eGFR, exploring its potential effect. All analyses will be performed using SAS version 9.4 (SAS Institute, Cary, NC, USA).
- **Descriptive statistics:** Descriptive statistics of baseline characteristics and outcomes variables will be provided for all enrolled participants; mean and standard deviation for continuous variable and proportion for categorical variable. Summaries will be provided for the full cohort and for subgroups defined by age, gender, and baseline kidney function. Highly-skewed variables may be transformed prior to statistical analyses to better approximate normality. Change over time in outcome variables will be presented by using appropriate charts and tables.
- **Analysis Plan for Aim 1:** The goal of this aim is to compare changes from baseline to 12 months in  $FMD_{BA}$  and aPWV between the two groups and ANCOVA will be used to test the difference. In all analyses, a  $p \leq 0.025$  will be considered significant. Furthermore, we will investigate how  $FMD_{BA}$  and aPWV change over time in one year by using longitudinal data analysis with mixed effect models. We will perform analysis of response profile in which we will assess the mean level of  $FMD_{BA}$  and aPWV at all time points in each group and examine for differences between groups at each time point. In addition, will assess for an effect of the intervention vs. placebo prior to the end of study. We will also fit parametric curves if exploratory analyses find a curve pattern of change over time in  $FMD_{BA}$  and aPWV.

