  - **Sodium bicarbonate** is an FDA approved medication for the treatment of metabolic acidosis and as an antacid. It is extremely well tolerated. The main side effect of oral sodium bicarbonate is flatulence and gastric distension. Metabolic alkalosis and weight gain from water retention can also occur but are rare. Serious reactions are uncommon with oral administration of the drug but include edema, CHF exacerbation, hypertension, hypernatremia, hypokalemia and pulmonary edema. Patients will be monitored monthly for side effects (see data and safety monitoring plan below).
  - **Nitroglycerin** may cause a slight decrease in arterial blood pressure, minor symptoms such as lightheadedness, tingling in the tongue and in the arms and legs, headaches, fainting and/or increased heart rate. The dose of nitroglycerin used is considered safe in the proposed population and is also used in patient populations to relieve angina.

There are no alternative methods that would provide the same type and accuracy of information as the state of-the art procedures proposed in this application.

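### The monthly GI tolerability questionnaire, as described, leaves out two of the three GI effects the plan expects, including flatulence

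*Combined protocol and SAP*

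**What the plan says.** All the relevant text is in the combined protocol and SAP.

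- **The instrument.** Under measures of adherence and safety, section 8 (Data Collection) says: "A GI symptoms questionnaire will be performed to assess tolerability of the intervention monthly". It may be given by telephone or in person. Its content is described in one sentence: "Participants will be asked to rate symptoms of nausea, bloating, and diarrhea".
- **The expected effects.** Section 7 (Safety monitoring) says: "Sodium bicarbonate therapy may cause bloating, flatulence and abdominal discomfort". The Data and Safety Monitoring Plan repeats this. The Medications text under Protection of Human Subjects says: "The main side effect of oral sodium bicarbonate is flatulence and gastric distension".
- **The monitoring commitment.** Of the expected events, section 7 says: "These expected adverse events will be monitored during the course of the study". Section 8 provides a second route: "Adverse event assessment will be performed monthly either via telephone or at an in person visit".
- **The analysis.** Section 11 (Statistical Analysis) covers the efficacy outcomes and adherence ("Compliance of intervention will be summarized using the number of pills taken as the proportion of planned number of pills"). It does not say how the GI ratings will be summarised.

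**The concern.** The questionnaire exists to measure tolerability, and the plan already says which GI effects it expects from the drug. One would expect the rated items to include those effects. As described, they include only one of the three. A symptom named as part of the main side effect is left to a general assessment, while two symptoms not named as expected are rated every month.

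What is at stake is the quality of the tolerability data. The opening section hopes to establish bicarbonate as a cheap treatment that is simple to take. The rationale for placebo, in the study drug dosing section, says that knowing the assignment could affect how side effects are perceived. A blinded, placebo-controlled trial of 108 patients is a good setting in which to learn how much flatulence and discomfort the drug causes. If those symptoms are not rated, a similar GI profile in the two arms would be hard to interpret for exactly the effects that were anticipated.

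**Working it through.** The plan states no figure on this point, and no sample size, power or alpha calculation depends on it. The check is an item-by-item comparison of the lists.

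| Symptom | Expected (section 7; Data and Safety Monitoring Plan) | Main side effect (Protection of Human Subjects) | Rated (section 8) |
|---|---|---|---|
| Bloating | yes | only if distension is read as bloating | yes |
| Flatulence | yes | yes | no |
| Abdominal discomfort | yes | no | no |
| Nausea | no | no | yes |
| Diarrhea | no | no | yes |

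1. Expected effects that are rated: 1 of 3 (bloating).
2. Expected effects that are not rated: 3 − 1 = 2 of 3 (flatulence and abdominal discomfort).
3. Rated items not listed as expected: 3 − 1 = 2 of 3 (nausea and diarrhea). Neither is named as an effect of the drug anywhere in the document.
4. Main side effect: flatulence is not rated. Gastric distension is close to bloating and is fairly treated as covered.
5. Other routes of capture: the adverse event assessment has the same monthly frequency as the questionnaire, so the two omitted symptoms can be recorded there. The document describes no symptom prompts and no rating scale for that assessment.
6. Items after the change: 3 existing + 2 new = 5.

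Flatulence and abdominal discomfort therefore have a route into the data, but a less structured one than the route given to nausea and diarrhea.

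**The case against.** Several points on the other side are sound.

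- **Bloating is covered.** A reader might infer that the questionnaire misses the symptoms the drug is expected to cause. That is too strong: bloating is rated, and gastric distension is close to it.
- **The omitted symptoms are not lost.** A reader might infer that they would be picked up only if participants volunteer them. The documents do not say this. Section 7 commits to monitoring the expected events, the Medications text promises monthly follow-up of side effects, and section 8 schedules the assessment monthly. Staff may well ask about these symptoms directly. The plan just does not say so, and gives them no rating.
- **No planned comparison is biased.** Section 11 specifies no between-arm GI analysis, and tolerability is not an aim or a primary or secondary outcome.
- **The size of any under-recording is unknown.** It is tempting to quote a shrunken difference between arms in percentage points. The documents give neither the symptom rates nor the fraction of cases the general assessment would catch, so any such figure would only return what was assumed.
- **The form is not reproduced.** Section 8 may summarise a longer questionnaire. This cannot be settled from the document.
- **Nausea and diarrhea are reasonable items.** Asking about them may reveal effects that were not anticipated.

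It could also be said that the pilot saw none of the expected events. But 0 of 16 patients gives a one-sided 95% upper bound of 1 − 0.05^(1/16) = 0.17, about 17%, after 6 weeks of treatment. The document does not say how symptoms were collected in the pilot, so it does not settle the rate of flatulence.

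These points limit the finding but do not remove it. The item list in section 8 and the expected-effect lists elsewhere do not match, and no section gives flatulence or abdominal discomfort a structured rating.

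**Conclusion.** The point holds in a limited form. As described in section 8, the questionnaire omits two of the three GI effects the plan expects, one of them part of the named main side effect. The loss is in structured, repeated rating of those symptoms. It is not a failure to record them at all, and it does not bias a planned test.

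The conclusion assumes that the sentence in section 8 is the full item list and that the adverse event assessment carries no rating of its own. If either assumption is wrong, the protocol text needs correcting rather than the form.

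The weight is minor. The case for acting is that the change is cheap and the trial is blinded. The primary outcomes, power and alpha are unchanged.

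**What to change.** - In section 8, add flatulence and abdominal discomfort to the rated symptoms, on the same scale and at the same contacts as the present items. Keep nausea, diarrhea and bloating.
- In section 11, add a sentence saying that all five ratings will be summarised descriptively by arm. No test is needed, so no multiplicity question arises.
- If the form in use already includes the two symptoms, correct the description in section 8 instead, and still add the sentence to section 11.

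The cost is two more questions on an existing questionnaire and a revision of the form, with no added visits. The downside is that participants already past some contacts will lack earlier scores for the new items. Summaries of those two items should use contacts from the change onward and state the number of participants contributing at each.

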**Table of Detailed Visits**

Screening Visit	Run-in period	Baseline Period	Follow-up Period Month 1 (in-person or remotely)	Follow-up Period Month 3, 6, 9	Follow-up Period Month 12
Medical history and physical examination	Height, weight, blood pressure, medication review	Height, weight, blood pressure, medication review	Height, weight, blood pressure, medication review	Height, weight, blood pressure, medication review	Height, weight, blood pressure, medication review
Informed consent	Titration of medications if blood pressure not at goal of < 130/80 mmHg	IV catheter, blood draw, 24-hour urine collection	IV catheter, blood draw, urine collection (optional)	Blood draw, urine collection	IV catheter, blood draw, 24-hour urine collection
Blood draw and urine collection		Blood vessel function and nitroglycerin	Blood vessel function and nitroglycerin (optional)	Adverse events assessed	Blood vessel function and nitroglycerin
Pregnancy test if indicated		Aortic pulse wave velocity measurement	Adverse events assessed	Pill count	Aortic pulse wave velocity measurement
		Cardiac MRI	Pill count	*6 month visit only: IV catheter, blood draw Blood vessel function and nitroglycerin Aortic pulse wave velocity measurement and 24-hour urine collection	Cardiac MRI
		Distribution of study drug			Adverse events assessed
					Pill count

## 9. Outcome Measures.

### a) Primary Outcomes

- **FMDBA:** Brachial artery FMDBA will be determined using high-resolution ultrasonography (Toshiba Xario 200) as described originally by Celermajer et al. and more recently by [name]. FMDBA will be measured at baseline, 1 month, 6 months and 12 months. ECG-gated end-diastolic ultrasound images and Doppler flow of the brachial artery will be acquired during baseline and FMDBA conditions. For FMDBA, reactive hyperemia will be produced by inflating a pediatric BP cuff around the forearm to 250 mmHg for 5 minutes followed by rapid deflation. Brachial artery endothelium independent dilation (EID) will be determined by measuring brachial artery dilation for 10 minutes after administration of sublingual nitroglycerin (0.4 mg). A commercially available software package (Vascular Analysis Tools 6.0 Medical Imaging Applications, LLC, Iowa City, IA) will be used to concurrently acquire ECG-gated brachial artery diameters. As recently recommended brachial artery dilation will be determined as the mm and % change from baseline diameter. Doppler blood flow velocity will be obtained at baseline and for 2 minutes after cuff release. Shear rate will also be calculated, and if group- or condition- differences exist, FMDBA will be adjusted accordingly. Of note, the PI of this proposal has already completed vascular measurements in 128 patients with CKD stages 3B-4 and thus has extensive experience with these measurements (K23 DK087859). The coefficient of variation for baseline and peak brachial diameter in our laboratory is 0.3% and 0.6%, respectively.
- **Large Elastic Artery Stiffness and Compliance:** Aortic PWV, a measure of large elastic artery stiffness, will be determined as described by Seals and colleagues at baseline, 6 months and 12 months. Briefly, transcutaneous custom tonometers (Noninvasive hemodynamics Workstation, Cardiovascular Engineering Inc., Norwood, MA) will be positioned at the aorta and femoral artery to measure PWV. Femoral and carotid compliance, also described previously by Seals et al. will be measured non-invasively using simultaneous high-resolution ultrasonography and applanation tonometry of the artery.

- b) **Justification for primary outcomes:** As discussed above, EDD and aPWV are key pathophysiological antecedents to LVH in patients with CKD. FMDBA is the most common, key, non-invasive technique used to assess EDD and aPWV is the gold standard measurement of arterial stiffness. Evaluating these outcomes will allow us to identify the intermediate vascular mechanisms by which bicarbonate administration may reduce the risk of CVD in patients with CKD. The PI and University of Colorado investigative team have expertise in these vascular function measurements.

### c) Secondary Outcomes

- **Left Ventricular Mass:** LVMI will be measured using gadolinium-free non-invasive cardiac MRI at baseline and 12 months. Cardiac MRI is the gold standard way to measure LVMI. Cardiac MRI will be performed on 3.0 T imaging system with cardiac sequence package using an electrocardiograph-gated, breath-hold, 2-dimensional, cardiac steady state free precession imaging for assessing ventricular volumes and function. All measurements will take place at the University of Colorado Brain Imaging Center, a research-dedicated facility with a 3 Tesla whole-body MRI scanner and a 3d/cardiac workstation for post-processing and calculation of LVMI. We will assess LVMI, LV end-diastolic and end-systolic volumes, relative wall thickness, left atrial size and ejection fraction. Transmural flow will be measured to further quantify diastolic dysfunction. LVMI will be calculated by normalizing LVM to height to the 2.7th power. LVM indexed to height has been strongly linked to outcomes in the CKD population. [name] (see letter of support), an experienced radiologist, will be reviewing the scans for safety and assessment of LVMI.

- **Plasma angiotensin II, aldosterone and endothelin-1:** Plasma AII, aldosterone and ET-1 will be measured by [name]. Plasma AII will be measured with Cayman EIA Kit, Cat No. 589301 (Cayman Chemical, Ann Arbor, MI). Plasma aldosterone will be measured with Cayman EIA Kit-Monoclonal, Cat (Cayman Chemical, Ann Arbor, MI). Plasma ET-1 will be measured with Enzyme Immunoassay Kit (Cayman Chemical, Ann Arbor, MI) after extraction using Bound Elut C18 columns (Varian, Harbor City, CA). [name] has extensive experience with these plasma tests and has successfully measured them in CKD populations.

- **Serum calcification propensity test:** A serum calcification propensity test (T50 assay) will be measured by [name] using a Nephelostart nephelometer (BMG Labtech, Offenburg, Germany), a label-free 96-well plate-based assay that measures the conversion of primary to secondary CPPs by detecting the time-resolved changes of laser light scattering (nephelometry) associated with it. [name] developed this

novel test of calcification and currently has the only laboratory in the world that performs the test. The analytical CV of a pooled serum precipitating at 270 minutes is 8.3%.

**d) Justification for secondary outcomes:** 1) LVH is very common in patients with CKD and is the strongest predictor of cardiovascular mortality in CKD patients. Cardiac MRI is the gold standard measurement of LVMI. 2) All, aldosterone and ET-1 increase with acid retention and are likely contributors to arterial dysfunction, LVH and VC. The long-term effect of alkali therapy on plasma All, aldosterone and ET-1 in CKD has not been evaluated. 3) The effect of alkali therapy on VC is unclear. We will measure  $T_{50}$ , a novel test that measures the overall calcification propensity of serum.  $T_{50}$  better defines the future calcification risk related to common abnormalities of mineral metabolism factors and improves prediction of calcification beyond single protein measurements.  $T_{50}$  predicts aortic stiffness, which is strongly linked to VC.

## 10. Power Calculations

**a) Aim 1:** Effect sizes were estimated for the primary endpoints of  $FMD_{BA}$  and aPWV based on published data of a similar population. We hypothesize that participants randomized to the bicarbonate group will have an improvement (i.e., increase) in  $FMD_{BA}$  at 12 months, while those in placebo will have a decrease in  $FMD_{BA}$ . We will compare change (from baseline to 12 months) in  $FMD_{BA}$  between the two groups. A previous study of paricalcitol vs. placebo in CKD stage 3-4 showed a between group difference of 1.8% in changed  $FMD_{BA}$  with 95% CI 0.3-3.1% after 12 weeks. Our preliminary data showed a between group difference (bicarbonate vs. control) of 1.6% in changed  $FMD_{BA}$  with 95% CI 0.2-2.9% after 6 weeks. Assuming a standard deviation of change of 0.8%, 54 patients in the placebo group and 54 patients in the bicarbonate group achieves 99% power to detect a 1.5% difference among the means (which is a clinically meaningful difference) using the two sample t-test with a two-sided 0.025 significance level (i.e. 5% significance level after Bonferroni correction for 2 outcomes) for intent-to-treat (ITT) analysis. It would also achieve 99% power to detect the same effect size in per-protocol analysis (n=45 per group allowing for 15% attrition). We hypothesize that participants randomized to the bicarbonate group will have no change or a decrease in arterial stiffness measured by aPWV at 12 months, while those in placebo will have an increase in stiffness. We will compare change (from baseline to 12 months) in aPWV between the two groups. In previous studies of CKD patients with comparable kidney function, the mean (SD) increase in aPWV was  $1.1 \pm 1$  m/s over a 12 month period. Assuming a common standard deviation within a group of 1.5 m/s, 54 patients in each group will provide 88% power to detect a 1.0 m/s difference among the means (which is a clinically significant difference) using the two sample t-test with a two-sided 0.025 significance level (i.e. 5% significance level after Bonferroni correction for 2 outcomes) for ITT analysis. It would also achieve 80% power to detect the same effect size in per-protocol analysis (n=45 per group allowing for 15% attrition).

**b) Aim 2:** Effect sizes were estimated for the outcome of LVMI (normalized to height to the 2.7th power) based on published data of longitudinal changes in LVMI. We hypothesize that participants randomized to the bicarbonate group will have a decrease in LVMI at 12 months whereas those in placebo will have no change or an increase in LVMI. We consider 5-g of between-group difference in absolute LV mass as clinically important based on previous studies where 10-g was considered for 2 years study duration, implying a mean between group-difference of 1.2 in LVMI, given mean height of 1.70 m. We further estimate the SD of the change in LVMI to be 1.8 based on information provided in the same study. Hence, 54 patients in each group will provide 93% power to detect a significant 5-g difference in absolute LV mass or a 1.2 g/m2.7 difference in LVMI between the two groups at 12 months using a two sample t-test with a 0.05 significance level.

**c) Aim 3:** We hypothesize that participants randomized to the bicarbonate group will have a decrease in plasma All, aldosterone and ET-1 12 months whereas those in placebo will have no change or an increase. Based on data from a small trial of alkali therapy in participants with CKD, we expect the mean ET-1 level to decrease by 0.9 pg/mL with a SD of 0.4 pg/mL and the mean aldosterone level to decrease by 20 pg/mL with a SD of 10.1 pg/mL from baseline to 12 months in the bicarbonate group. The planned sample size of 54 patients in each group will provide >95% power to detect the difference between the two groups. Based on published data in hypertensive patients with normal renal function, we expect the mean All level to decrease by 30% from baseline to 12 months in the bicarbonate group. The planned sample size of 54 patients in each group will provide >95% power to detect the difference between groups. There is very limited data regarding change in  $T_{50}$  levels in CKD patients. We hypothesize that the bicarbonate group will have an increase in  $T_{50}$  whereas the placebo will not change or decrease. Based on published data in CKD stage 3-4 patients, we expect the

baseline mean (SD) of  $T_{50}$  to be 329 (95) minutes. With a sample size of 54 patients per group, we have 95% power to detect a difference between groups if it is 0.7 SD of changed serum  $T_{50}$  from baseline (i.e. the effect size is 0.7) with a two-sided 0.05 significance level.

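### Testing FMD and aPWV each at a fixed 0.025 is valid, but Holm's step-down would give aPWV more power at the same 5% family-wise error

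*Combined protocol and SAP*

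**What the plan says.** Section 10a names two primary endpoints and tests each "using the two sample t-test with a two-sided 0.025 significance level (i.e. 5% significance level after Bonferroni correction for 2 outcomes".

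- **FMD:** "Assuming a standard deviation of change of 0.8%, 54 patients in the placebo group and 54 patients in the bicarbonate group achieves 99% power"; the target is "99% power to detect a 1.5% difference among the means".
- **aPWV:** "Assuming a common standard deviation within a group of 1.5 m/s", and "54 patients in each group will provide 88% power to detect a 1.0 m/s difference among the means". With losses: "It would also achieve 80% power to detect the same effect size in per-protocol analysis (n=45 per group allowing for 15% attrition".

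In section 11, the Aim 1 plan compares 12-month change by ANCOVA and sets p ≤ 0.025 for all its analyses. The sentence with that threshold ends, and the next begins, "will be considered significant. Furthermore, we will investigate how". So the longitudinal models, the comparisons at each time point and the look for an effect before the end of study sit under the same threshold. The general considerations make ANCOVA on complete data the primary analysis. Neither section describes a step-down or any other way of passing alpha from one outcome to the other.

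**The concern.** The threshold for each outcome stays at 0.025 whatever the other outcome shows. aPWV has the thinner stated power, 88% or 80%, against 99% for FMD. If FMD were clearly positive and aPWV came in at, say, p = 0.035, the plan would call aPWV non-significant. Holm would call it significant under the same 5% family-wise error that the plan has chosen. At stake is power on the weaker primary outcome, at no cost in patients or visits.

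**Working it through.** **Inputs (section 10a).** aPWV: difference 1.0 m/s, SD 1.5 m/s. FMD: difference 1.5%, SD of change 0.8%. 54 or 45 per group, two-sided 0.025. The 45-per-group row deserves weight, because the primary ANCOVA uses complete data and the plan allows 15% attrition.

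**Step 1: reproduce the plan's aPWV power.** Two-sample t-test, noncentrality = Δ / (SD × √(2/n)), with 2n − 2 degrees of freedom.

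| n per group | Noncentrality | Critical t at 0.025 / 0.05 | Power at 0.025 | Plan states | Power at 0.05 |
|---|---|---|---|---|---|
| 54 | 1.0 / (1.5 × 0.1925) = 3.464 | 2.274 / 1.983 | 88.1% | 88% | 93.0% |
| 45 | 1.0 / (1.5 × 0.2108) = 3.162 | 2.280 / 1.987 | 80.9% | 80% | 87.9% |

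Both stated figures are reproduced. FMD power with SD 0.8% exceeds 99.9% at either n.

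**Step 2: error control under Holm.** If both nulls are true, a false rejection needs the smaller p-value to be at or below 0.025. That is the same event as under Bonferroni, with probability at most 5% (simulated 4.9% at correlation 0 and 4.7% at 0.5). If only one null is true, that outcome is never tested above 0.05. The family-wise error is therefore at most 5% under any correlation.

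**Step 3: power under Holm.** aPWV is rejected if p ≤ 0.025, or if 0.025 < p ≤ 0.05 and FMD has p ≤ 0.025. With independent statistics:

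gain = (aPWV power at 0.05 − aPWV power at 0.025) × FMD power at 0.025.

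On the plan's inputs FMD power is essentially 1, so the gain is 4.8 points at n = 54 (to 93.0%) and 6.9 points at n = 45 (to 87.9%).

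**Step 4: sensitivity to the FMD SD.** The pilot interval in section 10a is 0.2 to 2.9%, from 16 crossover patients. Its half-width is 1.35, so the SD of the within-patient difference is 1.35 / 2.131 × √16 ≈ 2.5%. If the two periods are independent (an assumption), the SD of a single-period change is 2.5 / √2 ≈ 1.8%. Treating the FMD SD as an assumption, with zero correlation:

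| Assumed FMD SD | FMD power, n = 54 / 45 | aPWV gain in points, n = 54 / 45 |
|---|---|---|
| 1.8% | 97.9% / 95.1% | 4.7 / 6.6 |
| 2.5% | 79.9% / 71.4% | 3.9 / 4.9 |
| 3.0% | 62.8% / 53.8% | 3.0 / 3.7 |
| No FMD effect | 2.5% / 2.5% | 0.1 / 0.2 |

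At SD 2.5% and correlation 0.5 between the outcomes, the gain is about 2.7 and 3.4 points (normal approximation).

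**Step 5: sensitivity to the aPWV SD, with FMD always rejected.** At an assumed 1.25 m/s, power goes from 96.9% to 98.5% (n = 54) and from 93.3% to 96.4% (n = 45), gains of 1.6 and 3.0 points. At 1.0 m/s the gains are 0.1 and 0.4.

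**Step 6: the single-outcome error.** If FMD truly responds and aPWV does not, the aPWV false-positive rate is 2.5% under Bonferroni. Under Holm it is 0.025 × (1 + FMD power): 5.0% on the plan's inputs, and 4.5% (n = 54) or 4.3% (n = 45) at an FMD SD of 2.5%.

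**The case against.** The strongest reply is that nothing here is broken. Bonferroni is pre-specified and stated alike in sections 10 and 11, and the stated aPWV power is right. The Data and Safety Monitoring Plan also describes the study as less than fully confirmatory. All of that stands.

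A reader might go further than the documents allow in three ways.

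- **That the fixed 0.025 buys nothing.** It does buy something: it holds each outcome's own false-positive rate at 2.5%, and Holm gives that up exactly where its power gain is largest (step 6).
- **That the gain is 5 to 7 points as a general matter.** That size needs FMD power near 100% and an aPWV SD of 1.5 m/s. Section 10a itself also cites a 12-month aPWV increase of 1.1 ± 1 m/s, and ANCOVA may reduce the residual SD. The documents give no baseline correlation with which to quantify that.
- **That the change is free.** Holm has no simple matching simultaneous interval. A 97.5% interval for aPWV will include zero in the very cases where only Holm rejects (p between 0.025 and 0.05). An unadjusted 95% interval has no simultaneous coverage.

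None of these removes the advantage in power at the family-wise level that the plan has chosen.

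**Conclusion.** An optional improvement that is worth making; no defect in validity is shown. At the plan's 5% family-wise error, Holm can only add rejections. On the plan's inputs it adds 4.8 points of aPWV power at 54 per group and 6.9 at 45. Those figures rest on an FMD SD of 0.8%, an aPWV SD of 1.5 m/s and a t-test without covariate adjustment, and they should be read as close to the upper end. Under the less favourable assumptions above, the gain runs from about 5 points down to almost nothing, and it is never negative. The price is a looser error rate for a single outcome, still within 5%, and less tidy intervals.

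**What to change.** Before unblinding, make these changes in sections 10a and 11 (Aim 1):

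- **Primary tests.** State that, for the two 12-month ANCOVA comparisons of FMD and aPWV, the smaller p-value is tested at two-sided 0.025 and, if it is significant, the larger at two-sided 0.05 (Holm).
- **Other Aim 1 analyses.** Keep the 0.025 threshold for the longitudinal models, the time-point comparisons and the earlier-effect analyses. Replacing the present sentence outright would leave them with no stated level.
- **Power.** Restate aPWV power as 93.0% (54 per group) and 87.9% (45 per group), conditional on the FMD and aPWV inputs.
- **Intervals.** Say in advance which intervals will be reported. If 97.5%, note that they can include zero when Holm rejects. If 95%, label them unadjusted.
- **Error rate.** Acknowledge that the false-positive rate for one outcome can reach 5% when the other has a true effect.

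The cost is a few lines of text, with no added patients, visits or data. The timing is workable: no interim analysis is planned, and the study statistician stays blinded until the final analysis.
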